- Group 2: Joint Line Landmark Based (sham Ultrasound)
- Group 3: Suprapatellar Ultrasound Guided
- Group 4: Suprapatellar Landmark Based (sham Ultrasound)

The patients will be blinded to their group assignment prior to the first injection and will not be able to see which technique is employed. The provider performing the injections will not be blinded. The third injection (only) will be different in that contrast medium will be injected along with the hyaluronan. Following the third injection, fluoroscopy will be used to determine presence/absence of the contrast medium into the joint. The radiologist interpreting these images will be blinded to the technique employed. At 3 months following the third injection, the patients will be contacted by a surveyor blinded to the group assignment.

Objectives and Specific Aims

- 1. To compare the accuracy of injections into the knee joint with two different approaches, joint line and suprapatellar pouch
- 2. To determine if the addition of ultrasound guidance to traditional landmark-based techniques enhances the accuracy of these techniques
- 3. To examine differences in patient perceived pain and functioning of their knee joint following the injection series.

Medical Application

Injections into the knee joint are an exceedingly common procedure by a variety of specialists, primary care physicians, and non-physician clinicians. Knowledge of the most accurate and clinically effective injection technique will positively impact countless future patients. If we find that the addition of ultrasound guidance increases accuracy, as

we hypothesize, patient-oriented results should be better with fewer complications. This will allow the patient to return to activity quicker.

Background and Significance

Literature Review (as of 18 November 2010) and Preliminary Data and/or Findings.

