Patients randomized to the Suprapatellar Landmark (SPL) group will receive the same procedure as the Suprapatellar Ultrasound Guided (SPUS) group., with the exception of the sham ultrasound. To accomplish this, the ultrasound probe will purposely be positioned in the transverse plane of the suprapatellar area but the ultrasound display will be positioned so that the patient cannot visualize the screen, and the "FREEZE" button will be activated so that no active image is transmitted. The display will be positioned such that visualization by the patient will not be possible. The injecting physician will insert the needle lateral to the vastus lateralis toward the suprapatellar pouch. When the injecting physician believes the needle tip is in the pouch, the viscosupplement will be injected followed by the contrast.

It should be noted, that none of the participants in the study will be given the ability to visualize the ultrasound screen or injection procedure.

- 5. Following each injection, all patients will conclude their encounter with the injecting physician by being asked to rate on a scale of 0 to 10 their procedural pain from the procedure. For pain, a score of 0 will correspond to no pain and 10 will correspond to the worst pain they have ever experienced. After each injection, and at the three month follow up telephone call, the subjects will be asked to rate their overall procedure satisfaction on a 0-10 scale where "0" represents complete dissatisfaction and "10" represents complete satisfaction.
- 6. After the third injection, and after answering these questions, the patient will proceed directly to the Radiology Department.
- 7. Images of the joint will be obtained following the third injection. These images will be analyzed by a radiologist blinded to the technique employed and used to determine presence of or absence of the contrast medium within the joint.

Appointment 4 (telephone)

8. Subjects will be contacted approximately three months after the procedure by a Surveyor and the WOMAC Osteoarthritis Index will be repeated. The patients will be asked to rate their procedural satisfaction and also detail other therapies they have employed since the injection. This will include supplements, exercise (frequency and duration), acupuncture, physical therapy, etc.

Data Collection

Data collection will occur at three points during the investigation:

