• Initial evaluation: Screening instrument for first visit (history and physical, diagnostic and inclusion/exclusion criteria), WOMAC (prior to receiving each of the three injections), and intervention

The clinical staff will collect the following data:

- Name, email, phone number
- Demographics: age, gender, type and number of injections received previously
- Informed consent/HIPAA document
- WOMAC Osteoarthritis Index
- Post Procedure

The Injecting physician will record the following data:

- Group Assignment
- Amount and type of therapeutic substance injected
- Total time to complete procedure from sterilization to bandaging
- Procedural Pain Score (0 to 10)
- Procedural Satisfaction Score (0 to 10)
- Complications

In a separate electronic database, the radiologist will record the following data:

- Name
- Presence or absence of contrast material within the knee joint
- Three months after intervention (telephone)
 - WOMAC Osteoarthritis Index
 - Procedure Satisfaction Score (0 to 10)

Study Time Line

Assessment					
Study Day /	Initial Evaluation	and	Second	Third Injection	3 months
Period	First Injection		Injection	With contrast	Post Treatment
Screening	Х				
Informed	Х				
Consent, discuss					
Plan, etc.					
Randomization	Х				
Demographics,	Х				
History &					
Physical					
WOMAC (pre	х		Х	Х	Х
injection)					
Treatment	X		Х	Х	
Procedural Pain	Х		Х	Х	
(post injection)					
Procedural	Х		Х	X	Х

Satisfaction (post injection)			
Fluoroscopic Analysis		Х	
Complications (post injection)		X	

Statistical Consideration

Primary endpoints are presence/absence of contrast medium in the joint, the WOMAC osteoarthritis index, and overall satisfaction with the injection technique. Our statistical analysis of the WOMAC index will consider a mean change from baseline to post-injection with the variables of pain, stiffness, and function. We will also study the mean change of the Global Score from the WOMAC.

Data Analysis

Statistical analysis of the WOMAC score will consist of one-way analysis of variance (ANOVA) followed by Tukey's post-hoc multiple comparisons between the four groups with a 5%, two-sided familywise significance level (which allows for comparisons between all possible pairs of treatments). Chi square tests will be used to compare the percent accuracy among the four groups. We will also perform sub-analysis to determine if any trends can be linked to the type of medication (viscosupplementation) injected versus accuracy.

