Safety Monitoring and Analysis Plan

Since treatments are provided at the onset of the study, "stopping rules" will not apply in this study. Since the primary outcome includes pain and functioning at baseline and 3 months following the intervention, the entire study must be carried out in order to gather the desired data. There have been no unexpected side effects other than local pain and swelling at the injection site that have been reported in the studies using these injection techniques, so we do not believe any other specific side effects will need to be monitored. Patients will not be included in the study if a contraindication applies to them. Of note, viscosupplementation is not contraindicated in pregnant patients.

Sample Size Estimation

For the comparison of accuracy, a two group chi square test with a 5% two-sided significance level will have 80% power to detect a difference of 33 percentage points between groups when the accuracy in the less-accurate condition is 60% and the sample size in each group is 25.

Previous studies have demonstrated an effect size of the WOMAC ranging from 0.5 to 1.0 when medication interventions were studies on patients with knee pain. A sample size of 25 in each group will have 80% power to detect an effect size of 0.809 using a two group t-test with a 5% two-sided significance level.

Reference: Lenth, R. V. (2006-9). Java Applets for Power and Sample Size [Computer software]. Retrieved November, 2010, from http://www.stat.uiowa.edu/~rlenth/Power.

Reporting Adverse Events

Definitions:

Adverse events (adverse effects, adverse reactions): any occurrence of injury, dysfunction, disease, or abnormality of any organ or tissue that occurs in a subject enrolled in a clinical protocol. Manifestations of an adverse event may include symptoms, physical exam abnormalities, diagnostic study abnormalities, and/or death.

Expected adverse events: adverse events previously known or anticipated to result from: 1) the interventions and interactions used in the research (these events must be included as potential risks in the consent form); 2) the collection of identifiable private information under research (these events must be included as potential risks in the consent form); 3) an underlying disease, disorder, or condition of the human subjects; and/or 4) other circumstances unrelated to the research or any underlying disease, disorder, or condition of the subject.

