Unexpected adverse events /Unanticipated problems: adverse events that 1) are not expected given the nature of the research procedures and the subject population being studied; and 2) suggest that the research places subjects or others at a greater risk of harm or discomfort related to the research than was previously known or recognized.

Serious adverse event: an adverse event that is fatal, life-threatening, permanently disabling, require inpatient hospitalization, or result in congenital anomalies/birth defect, overdose or cancer, or any other adverse event that, based on appropriate medical judgment, may jeopardize the subject's health and may require medical or surgical intervention to prevent one of the other outcomes listed above.

Expected Adverse Events from Research Risks and Reporting

- Rare but serious (Event Rate < 1%): infection at the site of injection; contrast dye allergic reaction.
- Likely (5% ≤ Event Rate < 10%): 8% incidence of pseudo-synovitis with the use of Synvisc® products.
- More likely (Event Rate ≥ 10%): bruising, swelling and increased pain at site of injection for several days to a few weeks.

Monitoring of adverse clinical events will be done during each of the two scheduled followup assessments. These will be managed as follows:

- Infection at injection site, or blood-borne infection: manage as clinically indicated based on assessment by physician.
- Contrast dye reaction: treat as clinically indicated based on severity.
- Pseudo-synovitis: NSAIDs, ice, compression, elevation.
- Bruising, swelling and increased pain at site of injection: treat with compression, ice, and prescribed pain medications (no NSAIDs), and patient reassurance that these resolve with time.

Reporting Serious and Unexpected Adverse Events to the IRB

Serious Adverse Events: The PI, within one working day, will report all serious adverse events (SAE) occurring in subjects enrolled in the study. This is accomplished by submitting an adverse event report memorandum to the IRB. Serious adverse events will be reported even if the PI believes that the adverse events are unrelated to the protocol.

Unexpected (but not serious) adverse events occurring in subjects enrolled in the study, in the opinion of the PI, are possibly related to participation in the protocol will be reported by the PI within 10 (ten) working days to the IRB using the same procedure.

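### Adverse-event monitoring is promised at two follow-ups that are never identified, and expected non-serious events have no collection item after the third-injection visit

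*Combined protocol and SAP*

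**What the plan says.** Expected Adverse Events from Research Risks and Reporting makes the commitment: "Monitoring of adverse clinical events will be done during each of the two scheduled followup assessments". The two assessments are neither named nor dated. The same section lists the events it expects:

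- site infection and contrast allergy, each below 1% and described as rare but serious;
- pseudo-synovitis, 8% with Synvisc products;
- bruising, swelling and increased pain at the site, 10% or more, lasting from days up to some weeks.

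Data Collection opens with "Data collection will occur at three points during the investigation". These appear to be the initial evaluation, post procedure and three months. Complications are in the injecting physician's post-procedure list. In the Study Time Line, the row that begins "Complications (post injection" carries one mark.

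For Appointment 4 the protocol says: "Subjects will be contacted approximately three months after the procedure by a Surveyor and the WOMAC Osteoarthritis Index will be repeated". It continues: "The patients will be asked to rate their procedural satisfaction and also detail other therapies they have employed since the injection". The data list under "Three months after intervention (telephone" holds only the WOMAC and the satisfaction score.

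The Safety Monitoring and Analysis Plan refers to local pain and swelling in earlier studies and concludes: "we do not believe any other specific side effects will need to be monitored".

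**The concern.** The monitoring commitment cannot be matched to the schedule. Whoever builds the case report forms from the time line and data lists would find one complications entry and nothing on the 3-month form. By the protocol's own account, the commonest reactions outlast the visit at which the injection is given.

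The third injection matters most. It is the only one with contrast, and Human Use Justification names contrast reaction as the only risk the study adds to usual care. After it the patient goes straight to Radiology, where the radiologist's data list has no complications field. The next contact is about three months later.

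The stake is the completeness of the safety record. Medical Application also anticipates that if guidance improves accuracy, "patient-oriented results should be better with fewer complications". Counts collected this way would say little about that expectation, even descriptively.

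**Working it through.** **Step 1: which contacts could be the two assessments?** The contacts after the first injection visit are injection visit 2, injection visit 3 and the 3-month call.

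| Reading of follow-up assessment | Count | Matches two? | Item for expected non-serious events after the third-injection visit |
|---|---|---|---|
| Contacts after the third-injection visit | 1 (call) | No | None listed |
| Data-collection points after the initial evaluation | 2 (post procedure, 3 months) | Yes | Call is a monitoring point, but its list has no such field |
| Injection visits 2 and 3 | 2 | Yes | None; monitoring ends at visit 3 |
| All contacts after the first visit | 3 | No | None listed |

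Two readings reproduce the stated count. Neither supplies a collection item after the third-injection visit. Nor does the protocol state a question at visits 2 and 3 about events since the previous injection.

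**Step 2: where does the time-line mark sit?** The complications mark stands in the same position as the fluoroscopy mark, and the text places fluoroscopy only after the third injection. The row is also labelled as post-injection. The third-injection column is therefore the likely one, but the table breaks across a page and the original must be checked. If the mark is under 3 months, the time line would name the call as a monitoring point. The gap would then narrow to a disagreement with the 3-month data list.

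**Step 3: do the IRB duties fill the gap?** Serious events in any enrolled subject are reported within one working day. Unexpected, possibly related events are reported within ten. Neither duty is tied to a visit. Pseudo-synovitis and local reactions are on the protocol's expected list, so when they are not serious they fall under neither duty.

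**Step 4: scale.** Inputs are 120 participants in four groups of 30 (Study Design) and the rates in the adverse-event section.

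- Pseudo-synovitis, if every participant receives a Synvisc product: 120 × 0.08 = 9.6, or 30 × 0.08 = 2.4 per group. If none does, the stated rate implies 0. The protocol does not fix the product.
- Local reactions: at least 120 × 0.10 = 12, or 30 × 0.10 = 3 per group.
- Contrast allergy: fewer than 120 × 0.01 = 1.2.
- Share after injection 3, taking the rates as per participant and assuming an even spread over three injections: up to 9.6 / 3 = 3.2 pseudo-synovitis cases and at least 12 / 3 = 4 local reactions.
- The protocol does not say whether its rates are per participant or per injection. If they are per injection, the figures after injection 3 alone are up to 9.6 and at least 12.

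**The case against.** The strongest reply is that this is a missing form field. Two sensible readings give two assessments, and under one of them the 3-month call is already a promised monitoring point. Serious and unexpected events are reportable at any time. Patients are also seen about a week after injections 1 and 2, and a late event could surface when they describe other therapies. All of this stands as far as it goes, but these routes are passive and none has a field for an expected, non-serious event after injection 3.

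A reader might infer several stronger things that the documents do not support:

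- **That the number two is plainly wrong.** It is undefined. The 3-month call is the only scheduled contact after the third-injection visit, but not the only possible follow-up.
- **That late complications are never collected.** Monitoring is promised and the IRB duties have no visit limit. What is missing is systematic collection of expected non-serious events.
- **That these events begin after the patient leaves.** The protocol gives a duration for local reactions but no onset time, and no timing for infection or pseudo-synovitis. It also sets no completion time for the physician's complications entry.
- **That the Safety Monitoring section contradicts the expected-event list.** Its sentence concerns unexpected side effects seen in earlier studies, whereas the list concerns expected ones. The wording is loose and should be aligned.
- **That a planned comparison is biased.** Complications are not a primary endpoint and no between-group analysis of them is planned. The remark about fewer complications is a conditional expectation.

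It is also fair to say that recall at three months is a weak instrument for bruising that lasted days.

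**Conclusion.** The point holds in a limited form and should be corrected. Adverse-event monitoring is promised at two assessments that are not identified. On either reading that gives two, expected non-serious events after the contrast injection have no collection item.

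The counts in the working are events that may arise, not events shown to be missed. They rest on full enrolment, the protocol's own rates, the unknown product mix and, for the share after injection 3, the assumed even spread. The conclusion about the time line also rests on the complications mark being in the third-injection column. The effect is an incomplete safety record; the planned accuracy, WOMAC and satisfaction analyses are unaffected.

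**What to change.** Reconcile Appointment 4, Data Collection, the Study Time Line and the adverse-event section:

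1. Replace the reference to two assessments with named time points.
2. Record complications after each of the three injections.
3. At visits 2 and 3, ask about events since the last injection.
4. At the 3-month call, add an adverse-event question after the WOMAC and satisfaction items, so that recalling an event does not colour those answers.
5. Mark all of these in the time line and add the item to the 3-month data list.
6. Report complication counts descriptively by group.
7. Reword the Safety Monitoring sentence on which side effects are monitored so that it agrees with the expected-event list.

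The cost is a small protocol and form edit and a few extra questions at contacts that already take place. Brief reactions will be recalled imperfectly at three months, and the report should say so. The change concerns data collection only and leaves clinical management as it is.

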- **a.** There will be a Research Coordinator at the trial site who will administer the consent and HIPAA authorizations. This will be performed with a standardized consent form (Appendix A), including a scripted discussion of the study procedures and a scripted discussion of risks inherent in the injection techniques
- **b.** Upon completion of consent, the Coordinator will have the subject explain their understanding of the concept of treatment in their own words to ensure the subjects understand the consent.

Study Design

The study will be a randomized, double-blinded clinical study comparing four techniques for intra-articular knee injections.

The study investigators will receive a list of 120 computer generated random numbers from

Page 8 of 17 Version 2.0 one to four. No more than 30 will be in each group to ensure that each group is the correct size. Upon entry into the study, and prior to the first injection, subjects will randomized by selecting a sealed envelope from a box containing an equal number of envelopes for each of the four treatments groups. The envelope will be given, unopened, to the study doctor. The subject will be blinded to their study group assignment.

Double-blinding will be done as follows: The subjects will be blinded to whether ultrasound was used to guide their treatment. The radiologist, who will review the fluoroscopic images after the injections, will be blinded to treatment group assignment. The injecting physician will not be blinded to the treatment group assignment. Treating physicians (injecting physicians) will perform the technique as detailed below based on the assignment of the participant. Subjects and the radiologists will both be asked to guess their treatment group at each point in the data collection to determine the effectiveness of the blinding process. The Surveyor will also be blinded to the treatment group allocation.

The injecting physicians will consist of orthopedic surgeons, sports medicine fellows, or sports medicine fellowship trained primary care physicians. All injecting physicians will receive a minimum of 2 hours of hands-on training specific to the procedures employed in this study. Additionally, they will be supervised for their first several ultrasound-guided procedures to assure competence with the techniques.

Study Methodology/Procedures

Appointment 1

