1. Based on usual standard of care for knee pain, the treating physician will determine whether a series of viscosupplemental intra-articular knee joint injections is recommended. Patients who would likely benefit from the injections will be invited to participate in the study but will still receive usual care if they decide not to participate.

2. The informed consent document will be reviewed with and signed by interested patients.

Participants will complete the Western Ontario and McMaster Universities Arthritis Index (WOMAC), a validated, widely used instrument that measures self-reported pain, joint stiffness, and physical function. This index consists of 24 questions (5 pain, 2 stiffness, 17 physical function) and takes less than 5 minutes to complete. Raw scores are normalized to fit within a range of 0 (worst) to 100 (best). Additionally, there is a normalized raw Global Score that considers the variables of pain, stiffness, and physical function as a collective. The WOMAC will be issued four times during the study; prior to the three injections and again at the three month follow up phone call.

- 3. The injection procedure will be completed based on group assignment (see below). For the third injection in the series, all four groups will receive a "one needle, two syringe" injection as follows:
 - a. A 21 gauge two inch needle attached to a 5 ml syringe filled with 5 ml of Omnipaque 300 ® (General Electric Healthcare, Princeton, NJ) contrast medium will be introduced into the skin at the predetermined site and directed either with or without ultrasound guidance based upon group assignment. Injection site, landmarks, and intended path of the needle are detailed further in the group description below.
 - b. The entire contents of the syringe will then be injected. Following delivery of the contrast medium, the syringe will be removed while the needle remains in place.
 - c. A second syringe with the pre-determined medication (Hyaluronic Acid) will be attached to the needle and this medication will be delivered.
 - d. The needle and syringe will be removed from the knee and the injection will be bandaged.
- 4. The first and second injections will be performed based on the group assignment (see below) but will not include the use of contrast medium.

Group 1: Joint Line Ultrasound (JLUS)

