The Joint Line Ultrasound (JLUS) group will receive a standard medial or lateral joint line injection aided by ultrasound guidance. Specifically, this technique will entail palpation by the clinician of the soft tissue triangle formed by the tibial plateau, border of the patellar tendon, and the distal femoral condyle as found on both the medial and lateral joint line with the patient sitting on the edge of an examination table. Their knees will be bent to 90 degrees of flexion. The decision between a medial versus a lateral approach will be made by the provider performing the injection and based on the patient's anatomy and the provider's determination of the most facile side in which to perform the injection, as is the traditional practice of performing this technique. The triangle felt to be most prominent (i.e. largest joint space) will be chosen as the injection site. The area will be prepped in the usual sterile fashion.

The injection will be performed as detailed above with real time ultrasound guidance. To accomplish this a 10 MHz linear array transducer from a standardized ultrasound unit (Logiq E ®, General Electric Healthcare, Chalfont St. Giles, United Kingdom) will be placed in an oblique orientation on the opposite soft tissue triangle from the intended injection site so that

the inner aspect of the opposite femoral condyle is visualized, but the ultrasound display will be positioned so that the patient cannot visualize the screen. The injection will occur through the soft tissue triangle and directed at a 45 degree angle to the inner aspect of the opposite femoral condyle, with the needle being advanced parallel to (in the longitudinal axis of) the US probe. When the needle is visualized to be adjacent to the articular cartilage, a small bolus of saline will be injected. When the provider is satisfied that the needle tip is underneath the synovium overlying the condyle, as evidence by the saline easily dispersing underneath the synovium and not accumulating adjacent to it, the viscosupplement will be injected followed by the contrast.

Group 2: Joint Line Landmark (JLL)

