For all serious and/or unexpected adverse events, the PI will forward a copy of the adverse event report to IRB. A summary of all serious or unexpected side effects also will be included in the APR.

Protected Health Information

All participant PHI and study results will be located in a password protected spreadsheet on a computer. The radiologist will also maintain a password protected spreadsheet on his/her personal work computer with password protected access and will provide this data as requested to the Principle Investigator. The Principle Investigator will maintain a central file of all PI and data on a password protected spreadsheet on a computer with password protected access.

Research documents that contain PHI will be destroyed when the study results have been published in a medical journal. Non-PHI results will be maintained indefinitely in the possession of the PI.

Reporting Protocol Deviations

Any protocol deviations during the course of the study will be promptly reported to the IRB and sponsor if applicable, through the medical monitor of the protocol if applicable. Examples of deviations include but are not limited to variances from the treatment schedule for an individual patient, failure to use the most current consent form, and/or incomplete or lost records.

Reporting protocol deviation is accomplished by submitting a protocol deviation memorandum to the IRB.

Cost

The trial participants will not be charged any fees above the typical cost of their encounter with their physician and the cost of the injection of their medication. The expected cost of the Omnipaque 300 will be \$6.25 per injection, totaling \$750.00 for the entire study (\$6.25 x 120 participants). [name] will provide accomplishment and interpretation of the fluoroscopic images at no additional charge.

References

2. Arthritiscenter.com [Internet]. Arthritis Center of Connecticut. Available from: http://www.arthritiscenter.com/html/joint_injection.php.

3. Aafp.org [Internet]. American Family Physician. Available from: http://www.aafp.org/afp/2002/1015/p1497.html.

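### Reader blinding to joint line versus suprapatellar approach is promised but unprotected: one party is to obtain and read the fluoroscopy, and the visible puncture site differs by approach

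*Combined protocol and SAP*

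**What the plan says.** Three sections promise a blinded reader:

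- Methodology/Technical Approach: "The radiologist interpreting these images will be blinded to the technique employed".
- Study Design: "The radiologist, who will review the fluoroscopic images after the injections, will be blinded to treatment group assignment".
- Study Methodology/Procedures, step 7: "These images will be analyzed by a radiologist blinded to the technique employed".

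The Cost section says that one party, whose name is removed, "will provide accomplishment and interpretation of the fluoroscopic images at no additional charge".

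The patient's path to imaging is set out in Study Methodology/Procedures. Step 3d, on the third injection, ends: "The needle and syringe will be removed from the knee and the injection will be bandaged". Step 6 then says that, once the pain and satisfaction questions are answered, "the patient will proceed directly to the Radiology Department".

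The group descriptions put the puncture in different places. For the joint line groups it is one of the soft tissue triangles beside the patellar tendon: "The triangle felt to be most prominent (i.e. largest joint space) will be chosen as the injection site". For the suprapatellar groups it is anterolateral, about 1 cm above the patella.

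Study Design also plans for radiologists to guess the treatment group, as a check on blinding. Data Collection lists only two items for the radiologist to record: the patient's name and whether contrast was in the joint.

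**The concern.** Whoever stands at the fluoroscopy table can see where the knee was punctured, and so can tell joint line from suprapatellar. If that person also scores the images, the promise of a reader blind to technique is not secured for approach. The masking that the protocol does describe (screen turned away, image frozen) is aimed at the patient.

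Contrast in the joint is a primary endpoint, and the comparison of approaches is Aim 1. The score is binary. The protocol gives no rule for partial or peri-articular contrast and plans no second reader, so some images may need judgement. The literature review also states a directional expectation: with about 10 ml of fluid present, the ultrasound-guided suprapatellar technique should be the most accurate. Blinding is there to keep such an expectation out of borderline reads.

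**Working it through.** **1. What each part of the path reveals**

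| Feature | Joint line groups (1, 2) | Suprapatellar groups (3, 4) | Visible at imaging? |
|---|---|---|---|
| Puncture site | Beside the patellar tendon, medial or lateral | Anterolateral, about 1 cm above the patella | Yes, unless covered |
| Guidance | Live (1) or frozen image (2) | Live (3) or frozen image (4) | No; same puncture region within an approach |

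The exposure is to approach (Aim 1). A bandage does not show whether the ultrasound was live, so Aim 2 is not affected by this route. No uniform dressing, drape, separate operator or coded image is described.

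**2. The plan's own accuracy figure**

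Inputs (Sample Size Estimation): 60% versus 60 + 33 = 93%, 25 per group, two-sided 5%. The mean proportion is 0.765.

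- SE under no difference: √(2 × 0.765 × 0.235 / 25) = 0.120
- SE under the alternative: √((0.60 × 0.40 + 0.93 × 0.07) / 25) = 0.110
- Power: Φ((0.33 − 1.96 × 0.120) / 0.110), which is 0.805 with unrounded SEs

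The stated 80% reproduces. This point does not dispute it.

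**3. What a tilted reading would do**

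Assumptions, none of them in the documents: true accuracy is 80% in all four arms, and reading shifts the scored accuracy of one approach by *b*. From Study Design: 120 participants, at most 30 per group, hence 60 per approach. The variance is held at 0.8 × 0.2 = 0.16, so the results are approximate.

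*Four-group chi-square test (the test in Data Analysis; 3 df, critical value 7.815).* Each arm lies b/2 from the overall mean, so the noncentrality is λ = 4 × 30 × (b/2)² / 0.16.

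- b = 2.5 points: λ = 0.117
- b = 5 points: λ = 120 × 0.025² / 0.16 = 0.469
- b = 10 points: λ = 120 × 0.05² / 0.16 = 1.875

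*Pooled comparison by approach, 60 versus 60 (not specified in Data Analysis, but a direct test of Aim 1).* SE = √(2 × 0.16 / 60) = 0.073. Rejection probability = Φ(b/SE − 1.96) + Φ(−b/SE − 1.96), with b/SE = 0.34, 0.68 and 1.37.

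| Tilt | Images out of 60 | Four-group test | Pooled 60 v 60 |
|---|---|---|---|
| 0 | 0 | 5% | 5% |
| 2.5 points | 1.5 | 5.7% | 6.4% |
| 5 points | 3 | 7.9% | 10.5% |
| 10 points | 6 | 18% | 28% |

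**4. A second bias model**

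Suppose instead that a share *m* of true suprapatellar misses is scored as hits, so that scored accuracy is p + m(1 − p). For the pooled 60 versus 60 test, m = 10%, 20% and 30% give false-positive rates of about 7%, 15% and 28% if true accuracy is 60%, and about 6%, 8% and 11% if it is 85%. The range is similar, and the result again depends on a quantity that the documents do not supply.

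**The case against.** The strongest reply is that the link between operator and reader rests on one word in a cost statement. The party's name is removed, and accomplishment could mean arranging the imaging. The operative sections say that images are obtained and then analysed, which fits a technologist at the table. Nor is the size or type of bandage given; a knee wrap would hide the site. All of this stands, and it limits the conclusion. It does not close the gap, because no section says who acquires the images or how the site is hidden from a reader who may be present.

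The protocol also has its own check, the radiologist's guess of group. It addresses this risk, but it can only show unblinding after the reads are made. The guess is not among the radiologist's listed data items, and Data Analysis does not mention it.

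Three stronger readings are tempting, and the documents do not support them:

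- **That blinding fails.** The text shows that blinding to approach is unprotected, not that it is broken.
- **That the patient could tell the radiologist which technique was used.** Patients are blinded to guidance and cannot see the screen or the procedure. At most they could say where they felt the needle.
- **That reads leak out before the 3-month call.** Protected Health Information says that the radiologist "will provide this data as requested to the Principle Investigator". It gives no timing and no route to the patient or the surveyor, and the surveyor is blinded. An effect on the later WOMAC or satisfaction scores would be speculation.

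**Conclusion.** The point holds as a gap in protection. As written, the plan leaves the reader of a primary endpoint exposed to the Aim 1 factor, and blinding to approach is likely to be compromised if the Cost sentence means what it appears to say. Blinding to live versus sham ultrasound is not in question.

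The size of any bias cannot be known from the documents. For the planned four-group test, the pooled figures of 10.5% and 28% would overstate the effect; about 8% and 18% apply, for tilts of 5 and 10 points. These figures rest on equal true accuracy of 80%, full enrolment of 30 per arm, and all the tilt running one way. A tilt of 2.5 points would hardly matter under either test. The change is worth making because it is cheap and makes the protocol's own promise deliverable.

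**What to change.** 1. **Reconcile the sections.** Bring Cost into line with Study Design and step 7: state who acquires the images, who reads them, and how the reader is kept blind to approach.
2. **Mask the site.** In step 3d, before the patient leaves for Radiology, apply matching dressings over both the joint line and the suprapatellar sites in every participant, and leave them on until imaging is done. Because the joint line side is the provider's choice, covering both triangles keeps the pattern the same in everyone.
3. **Separate reading from acquisition.** Have the radiologist score stored images, labelled by study number only, in a session apart from acquisition. Replace the name with the study number in the reading database.
4. **Use the blinding check.** Add the radiologist's guess to the listed data items, and report the guesses by approach as well as by group. With equal groups, chance agreement is 1 in 2 for approach and 1 in 4 for group.

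The cost is protocol wording, one or two extra dressings per participant and a slightly later accuracy result. No extra reader, procedure or participant is needed. The pattern of contrast, above all after a missed injection, may still hint at the approach, so these steps reduce unblinding but do not remove it.
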